8.3. Clinical Laboratory Tests

Descriptive statistics (N, mean, SD, median and range) for absolute values and changes from baseline will be provided by treatment group at each scheduled time point and endpoint for the clinical laboratory tests (hematology, chemistry and urinalysis). Laboratory summaries will be provided in Standard International (SI) units.

Cross-tabulations (with classes for below, within, and above the central laboratory range) showing the shift of laboratory values from baseline to each scheduled time point and endpoint will be presented by treatment group.

Clinical laboratory test values will be considered “treatment emergent markedly abnormal” (TEMA) using the criteria defined by the Sponsor (Johnson & Johnson Research & Development, LLC) listed in [Table 5](#). The identification of TEMA laboratory values is based on the post-baseline (after the start of double-blind study medication) value being out of range while the baseline value is either missing or within the range given in [Table 5](#). If post-baseline laboratory results are above the upper limit and the baseline value is below the lower limit, then the post-baseline abnormality will also be considered TEMA. The same applies to the post-baseline value being below the lower limit with the baseline value being above the upper limit.

The incidence of TEMA will be presented by treatment group at each scheduled time point, at endpoint, and at any time during the double-blind treatment phase.

Table 5: Laboratory Parameters: Criteria for Markedly Abnormal Values

Laboratory Parameter	Markedly Low	Markedly High
Albumin (g/L)	<20	> 2 x ULN
Alkaline phosphatase (U/L)	N/A	> 1.5 x ULN
Alanine aminotransferase (ALT) (U/L)	N/A	> 3 x ULN
Aspartate aminotransferase (AST) (U/L)	N/A	> 3 x ULN
Bicarbonate [mmol/L]	15.1	34.9
Bilirubin (umol/L)	N/A	> 1.5 x ULN
Blood Urea Nitrogen (mmol/L)	N/A	> 3 x ULN
Calcium (mmol/L)	<1.75	>3
Chloride (mmol/L)	<90	>120
Creatine kinase (U/L)	N/A	> 3 x ULN
Creatinine (umol/L)	N/A	> 1.5 x ULN
Gamma glutamyl transferase (U/L)	N/A	> 3 x ULN
Glucose (mmol/L)	<3.33	> 3 x ULN
Lactate dehydrogenase (U/L)	N/A	> 1.5 x ULN
Phosphate (mmol/L)	<0.484	> 1.5 x ULN
Potassium (mmol/L)	<2.8	>5.8
Protein (g/L)	N/A	> 2 x ULN
Prothrombin International Normalized Ratio	N/A	≥1.3
Sodium (mmol/L)	<125.0	>155.0
Hemoglobin (g/L)	<75	> 1.1 x ULN
Platelets (x10e9/L)	<100	> 3 x ULN
Erythrocytes (x10e12/L)	<3	> 2 x ULN
Leukocytes (x10e9/L)	<2.5	> 2.5 x ULN
Hematocrit [fraction]		
male	0.24	0.55
female	0.28	0.5

Graphical presentations will be created for the following liver function tests: alanine aminotransferase, aspartate aminotransferase, albumin, bilirubin, alkaline phosphatase, gamma glutamyl transferase. Liver function test results standardized to the upper limit of normal (based on central laboratory ranges) will be graphically presented over time for each subject. The incidence of liver function tests above the central laboratory normal limit will be presented by treatment group at each scheduled time point, at endpoint, and at any time during the double-blind treatment phase.

Graphical presentations will also be created for prothrombin international normalized ratio results.

Clinical laboratory tests that meet the criteria for abnormal and markedly abnormal will be listed by subject.

Results on urine drug screen, alcohol screen and pregnancy test will be presented in a listing.

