#### Footnotes:

- a. Visits should be conducted within +/-3 days of the scheduled day.
- b. If a subject discontinues treatment before the end of the double-blind treatment phase, early withdrawal (EW) and post-treatment assessments should be obtained. Follow-up visit will take place 7 to 28 days after last dose intake or early withdrawal.
- c. Prestudy therapy will include all medications taken within the 30 days before screening.
- d. Triplicate ECG at Day 1
- e. Supine blood pressure, pulse, and oral temperature. Following the supine vital sign assessment, orthostatic vital signs (blood pressure, pulse) will be taken after standing for at least 3 minutes.
- f. Body weight will be measured with subjects lightly clothed.
- g. Serum chemistry, hematology, coagulation and urinalysis.
- h. Only in case of any clinical significant abnormalities observed at Week 12.
- i ECG should be performed prior to study drug administration, and if possible, at approximately the same time of the day as the screening ECG.
- j Refer to study exclusion criteria for circumstances in which a repeat test during Screening is permitted.
- k Performed for all women. Serum and urine pregnancy test performed at Screening and Follow-up. At all other time points, if the urine pregnancy test is positive, a serum β-hcg test will be performed. Investigators may perform additional pregnancy testing at their discretion as clinically needed.
-  The HAM-A6 is a subscale derived from the SIGH-A (structured interview guide version of the HAM-A).
- m. At each time point, a venous blood sample will be collected for PK analysis of JNJ-42165279 concentration at predose (i.e., prior to morning dose on Days 14 and 28) and 2 hours postdose (only at Day 14).
- n. A 10 mL blood sample will be collected for the pharmacogenomics component of this study. A sample collected at a later time point does not constitute a protocol violation and would not require protocol amendment.
- o. A venous blood sample will be collected for the FAAs (AEA, PEA and OEA) and exploratory biomarkers. The Visit 2 sample must be taken before the first dose of JNJ-42165279 /placebo.
- p. Baseline version completed at Screening.
- q. HDRS17 anxiety/somatization factor score determined from the assessment.

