# Toxicology

The oral toxicity of JNJ-42165279 was characterized in 3-month toxicity studies in rats and dogs. In male rats at all doses, adverse effects on coagulation parameters (increased prothrombin time [PT] and activated partial thromboplastin time [aPTT]) and the reproductive organs (decreased sperm motility and abnormal sperm morphology) were observed. In female rats,

microscopic changes were observed in the kidney (mineralization and vacuolar degeneration) at  $\geq 25 \text{ mg/kg}$ , while there were no findings at the low dose of 5 mg/kg. Based on these findings, the no observed adverse effect level (NOAEL) could not be established in male rats and was 5 mg/kg in female rats. Relative to exposures at the anticipated clinically effective dose of 25 mg (Day 10 Cmax= 225 ng/mL and AUC = 2,204 ng.h/mL), Cmax and AUC exposures in the female rats provide 10-fold and 3.5-fold margins respectively. In dogs, doses of 5 and 15 mg/kg were well tolerated, while adverse effects at 100 $\rightarrow$ 50 mg/kg were noted in the liver and gall bladder (vacuolation with cellular degeneration or necrosis that correlated with mild increases in aspartate transaminase [AST], alanine aminotransferase [ALT], alkaline phosphatase [ALP], and gamma-glutamyltransferase [GGT]), thymus (atrophy), bone (hypercellularity of the erythroid cell line in sternal bone marrow), and epididymis/testis (decreased sperm numbers and secondary spermatid degeneration/depletion). Based on these findings, the NOAEL in dogs was 15 mg/kg, providing Cmax and AUC margins of at least 26-fold and 35-fold over those at the anticipated human effective levels.

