# 9.2.6. Clinical Laboratory Tests a

Blood samples (under fasted conditions whenever feasible) for serum chemistry and hematology and a random urine sample for urinalysis will be collected. The investigator must review the laboratory report, document this review, and record any clinically relevant changes occurring during the study in the adverse event section of the CRF. The laboratory reports must be filed with the source documents. The following tests will be performed a central laboratory appointed by the Sponsor:

Hematology Panel	
-hemoglobin -hematocrit - red blood cell (RBC) count - white blood cell (WBC) count with differential	
 
platelet count
 
mean corpuscular volume
 
mean corpuscular hemoglobin
 
mean corpuscular hemoglobin concentration
 

- Coagulation International normalized ratio (INR)
- -prothrombin time

-activated partial thromboplastin time (aPPT)

- Serum Chemistry Panel
  - -sodium -alkaline phosphatase -potassium -creatine phosphokinase (CPK) -chloride -lactic acid dehydrogenase (LDH) -uric acid -bicarbonate -blood urea nitrogen (BUN) -calcium -creatinine - phosphate -albumin -glucose -aspartate aminotransferase (AST) -total protein -alanine aminotransferase (ALT) -cholesterol -gamma-glutamyltransferase (GGT) -triglycerides -total and direct bilirubin -high density lipid protein -low density lipid protein

-magnesium

<sup>a This section has been amended per Amendment INT-3.

Urinalysis Dipstick Flow Cytometry -specific gravity -RBC -WBS -pH -glucose -epithelial cells -protein -blood -ketones Sediment -bilirubin -crystals -urobilinogen -casts -nitrite -bacteria -leukocyte esterase

Specific gravity, pH, glucose, protein, blood, ketones, bilirubin, and urobilinogen will be determined using a dipstick. RBC, WBC, epithelial cells, crystals, casts, and bacteria will be measured using flow cytometry. If there is discordance between the dipstick results and the flow cytometric results, the sediment will be examined microscopically.

- Urine Drug Screen: opiates (including methadone), cocaine, amphetamines, cannabinoids, barbiturates, and benzodiazepines.
- Serology (hepatitis B surface antigen (HBsAg), hepatitis C antibody (anti-HCV), HIV)
- Alcohol (blood) test

Pregnancy tests:

- In all women: serum β-HCG and urine pregnancy test will be performed at Screening and Follow-up and urine pregnancy test at study visits 2 and 9.

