### **Clinical Laboratory Tests**

Laboratory data will be summarized by type of laboratory test. Descriptive statistics will be calculated for each laboratory analyte at baseline and at each scheduled time point, and for changes from baseline.

The number and percentage of subjects experiencing a laboratory result below or above normal reference ranges will be provided for each laboratory analyte by treatment group. Summaries will be provided for all subjects receiving at least one dose of study drug in this study.

A listing of subjects with any laboratory result outside the reference ranges will be provided.

<sup>a This section has been amended per Amendment INT-2.

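### SAP 8.3 leaves coagulation out of the by-arm laboratory descriptive statistics, contrary to Protocol 11.4, and names aPTT in no laboratory output

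*SAP*

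**What the plan says.** **Collection.** Footnote g to the Protocol's Time and Events Schedule defines the clinical laboratory assessments as four panels: "Serum chemistry, hematology, coagulation and urinalysis". Protocol 9.2.6 lists coagulation under its own label, beginning "Coagulation International normalized ratio (INR"), followed by prothrombin time and "activated partial thromboplastin time (aPPT") (the protocol's spelling of aPTT).

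**Protocol analysis.** Protocol 11.4 (Clinical Laboratory Tests) says: "Descriptive statistics will be calculated for each laboratory analyte at baseline and at each scheduled time point", and extends this to changes from baseline. It also promises, for each analyte and by treatment group, the number and percentage of subjects outside the reference range.

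**SAP analysis.** SAP 8.3 gives descriptive statistics of values and changes from baseline by treatment group for the "clinical laboratory tests (hematology, chemistry and urinalysis"). It then plans by-arm shift tables against the central laboratory range, marked-abnormality (TEMA) criteria in Table 5, graphs, and a subject listing. Table 5 has one coagulation row, "Prothrombin International Normalized Ratio", with a markedly high limit of 1.3 or more. INR graphs are also planned.

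**Background.** Protocol 1.1 (Toxicology) reports "increased prothrombin time [PT] and activated partial thromboplastin time [aPTT") in male rats at all doses in the 3-month study.

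**The concern.** The SAP is the document from which the tables are programmed. Its list of panels omits exactly one of the four that the protocol collects, and it gives no reason. Someone following SAP 8.3 literally would produce no means or changes from baseline for INR, PT or aPTT, although Protocol 11.4 promises them for every analyte.

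The omitted panel has a non-clinical history. The sponsor took the rat finding seriously enough to add coagulation measurements to the second multiple-dose Phase 1 study, EDI1002 (Protocol 1.1, Clinical Studies). At stake is whether a modest drift in clotting times over 12 weeks, mostly within the normal range, would be visible in the study report by treatment arm.

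**Working it through.** The plan states no figure to reproduce. The check compares what is collected and promised with each output in SAP 8.3.

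**1. Collected.** Clinical laboratory assessments are scheduled at screening, Day 1, and Weeks 2, 4, 6, 8, 10 and 12, with follow-up samples only if Week 12 was abnormal. The visit lists in Protocol 9.1.2 to 9.1.4 name coagulation separately from hematology each time.

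**2. Promised (Protocol 11.4).** Two things are promised for each analyte: descriptive statistics with changes from baseline, and by-arm counts outside the reference range.

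**3. Planned (SAP 8.3), output by output.**

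| Output | INR | PT (seconds) | aPTT |
|---|---|---|---|
| By-arm descriptive statistics and changes from baseline | not named | not named | not named |
| By-arm shift tables against the laboratory range | not excluded, not named | not excluded, not named | not excluded, not named |
| By-arm TEMA incidence (Table 5) | yes | no row | no row |
| Graphs | yes | no | no |
| Subject listing of abnormal values | not restricted by panel | not restricted by panel | not restricted by panel |

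The TEMA row follows from "The incidence of TEMA will be presented by treatment group at each scheduled time point", which applies to whatever Table 5 contains. By-arm incidence above the normal limit is spelled out separately only for the liver tests. The protocol's out-of-range counts for PT and aPTT therefore depend on whether the shift tables include them.

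**4. What the remaining outputs can show.** Shift tables by range class, the INR limit in Table 5 and the abnormal-value listing all register only the crossing of a limit. A shift within the normal range shows in means and changes from baseline, or in plots of values. Plots are planned for INR, though SAP 8.3 does not say whether they are by arm. For aPTT neither means nor plots are planned, and INR, being a rescaled PT, does not measure it.

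**5. Earlier human data (Protocol 1.1, Clinical Studies).**
- EDI1001, repeat-dose part: 6 subjects on active drug at 100 mg for 6 days.
- EDI1002: four cohorts with 6 on active drug in each, so 4 × 6 = 24 on active drug, for 10 days; 6 of these received 25 mg.
- Both studies reported no changes or abnormal findings in coagulation parameters.
- This trial: 12 weeks = 84 days at 25 mg, and 84 / 10 = 8.4 times the longest of those repeat-dose periods. Enrolment of 137 in a 1:1 ratio puts about 68 subjects on active drug.

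The rat finding came from 3 months of dosing. This trial is closer to that duration and has a concurrent placebo arm, so it is the more informative place to look.

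**The case against.** The strongest reply is that the list of panels in SAP 8.3 is shorthand. The opening sentence of Protocol 9.2.6 also mentions only chemistry, hematology and urinalysis, and the section then goes on to list the coagulation tests. SAP Table 5 places INR among the chemistry rows, between protein and sodium. The SAP nowhere announces a departure from Protocol 11.4. This makes an oversight more likely than a decision. It does not supply the missing tables, because footnote g, the panel list in 9.2.6 and the visit lists treat coagulation as its own panel.

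Three stronger readings are tempting, and the documents do not support them.

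- *A reader might infer that the SAP ignores coagulation, or never compares PT or aPTT between arms.* INR belongs to the panel and gets by-arm TEMA incidence and graphs. The shift tables are by arm, refer to laboratory values generally, and can be read to include PT and aPTT.
- *A reader might infer a general animal signal with no safe dose established because of clotting times.* The finding was in male rats. The protocol describes no coagulation finding in female rats or dogs. The missing NOAEL in male rats rests on sperm findings as well.
- *A reader might try to express the loss as statistical power.* SAP 8.3 plans no hypothesis test on laboratory data, so a power figure would describe a test that nobody proposes.

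The negative Phase 1 results also stand and must be reported beside the rat finding. They lower the prior concern, but short dosing in small cohorts does not settle it.

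**Conclusion.** The mismatch is real and narrow. SAP 8.3 does not deliver the descriptive statistics and changes from baseline that Protocol 11.4 promises for INR, PT and aPTT. It leaves unclear whether the by-arm out-of-range information for PT and aPTT will appear. aPTT is the least covered: no laboratory output names it.

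Severity is minor. This is a safety-reporting gap, with no effect on the primary analysis, on data collection or on the listing of abnormal values. No numerical size attaches to it beyond one panel of four and three analytes. The conclusion assumes that SAP 8.3 is the full specification of the laboratory outputs; table shells that already include coagulation would reduce it to a correction of wording.

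**What to change.** In SAP 8.3, change the list of panels to *hematology, coagulation, chemistry and urinalysis*. State that the by-arm descriptive, change-from-baseline and shift tables include INR, PT and aPTT. For completeness, either give Table 5 a marked-abnormality criterion for aPTT or note that none applies. Extending the INR graphs to PT and aPTT is optional, since neither document requires it.

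The cost is one added word, a clarifying sentence and a few table rows from data already being collected. No protocol amendment is needed, because the change brings the SAP back into line with Protocol 11.4.

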# 3.3. Stopping Criteria

# 3.3.1. Individual Stopping Criteriaa

In this phase 2a safety study, the following individual stopping rules will apply:

- The investigator or sponsor believes (e.g. that for safety or tolerability reasons such as a serious adverse event at least possibly related to the study drug) it is in the best interest of the subject to discontinue the study.
- The subject becomes pregnant

<sup>a This section has been amended per Amendment INT-1.

- A subject will be discontinued from the study when the QTc interval is higher than 500 msec. ECG events should be confirmed by repeat twice as soon as possible after the initial ECG, and the average value of the QTcB interval will be used to determine whether a subject should be discontinued. The subject will continue to be monitored by repeated 12-lead ECGs (at least every 60 min) until the ECG normalizes.
- Because of limited information on the effects of JNJ-42165279 on the human liver function a subject will be discontinued from the study if either of the following occur:
  - Aspartate transaminase (AST) and/or alanine transaminase (ALT) >3 x Upper Limit of Normal (ULN) (confirmed by repeat),
  - Total bilirubin >2 x ULN (confirmed by repeat).

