- 7. Subject has a clinically significant abnormal finding on 12-lead ECG such as QTc >450 msec for males and females, Left Bundle Branch Block, AV Block second degree or higher, permanent pacemaker or implantable cardioverter defibrillator (ICD) at screening or baseline (Day 1 predose), or any finding which in the opinion of the investigator is not appropriate and reasonable for the population under study. ECG recordings and vital signs may be repeated once and for questions on findings on the ECG a local cardiologist should be consulted.
- 8. Subject has a history of or current liver or renal insufficiency; clinically significant cardiac, vascular, pulmonary, gastrointestinal, endocrine, hematologic, rheumatologic, psychiatric, or metabolic disturbances (e.g. unstable situation needing monitoring or regular dose adaptations). Subjects with liver function analytes higher than the upper limit of normal at baseline should be reviewed with the sponsor. If the subject has any liver function tests >2 times the upper limit of normal, he/she should not be enrolled.
- 9. Subject has a history of malignancy within 5 years before screening (exceptions are squamous and basal cell carcinomas of the skin and carcinoma in situ of the cervix, or malignancy that in the opinion of the investigator, with written concurrence with the sponsor's medical monitor, is considered cured with minimal risk of recurrence).
- 10. If a subject is using a drug with moderate/strong CYP3A4 inhibiting properties at, or prior to, Screening it must be discontinued at least within 1 month prior to Day 1. Note: an existing medication should not be stopped solely for the purpose of the subject entering the study. Moderate and strong inducers of CYP3A4 are prohibited during the study (See Attachment 13).
- 11. Subject has a history of positive tests for hepatitis B surface antigen (HBsAg) or hepatitis C antibody (anti-HCV) positive, or other clinically active liver disease, or tests positive for HBsAg or anti-HCV at Screening.

- 12. Subject tests positive for human immunodeficiency virus (HIV) or antibodies at Screening and is not being treated. Subjects with known HIV infection who are being treated, have shown a good response, are otherwise clinically stable, and can continue to comply with treatment may be enrolled. Subjects requiring treatment with medications that are moderate or strong CYP3A inhibitors (such as most protease inhibitors: see Attachment 13) must be excluded.

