2.3.3. Baseline

Baseline is defined as the last non-missing observation prior to first dose of study drug.

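### The SAP's markedly-abnormal rule cannot count worsening bilirubin or alkaline phosphatase in an eligible subject whose baseline lies above 1.5 and up to 2 x ULN

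*SAP*

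**What the plan says.** **Counting rule.** SAP 8.3 bases TEMA on the post-baseline "value being out of range while the baseline value is either missing or within the range given in" Table 5. The only other route is a switch from one extreme to the other: "If post-baseline laboratory results are above the upper limit and the baseline value is below the lower limit", or the mirror case. The Table 5 row reads "Bilirubin (umol/L) N/A > 1.5 x ULN". ALP has the same high limit and no low limit. ALT, AST and GGT have a high limit of 3 x ULN.

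**Baseline.** SAP 2.3.3: "Baseline is defined as the last non-missing observation prior to first dose of study drug".

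**Entry.** Protocol 4.2, exclusion 8: "Subjects with liver function analytes higher than the upper limit of normal at baseline should be reviewed with the sponsor". It continues: "If the subject has any liver function tests >2 times the upper limit of normal, he/she should not be enrolled". A value above ULN and up to 2 x ULN is thus reviewed but not barred.

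**Discontinuation.** Protocol 3.3.1 lists, as one of two liver criteria, "Total bilirubin >2 x ULN (confirmed by repeat").

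**Other liver output.** SAP 8.3 also says "The incidence of liver function tests above the central laboratory normal limit will be presented by treatment group". It plans shift tables (below, within, above), individual plots standardized to ULN, and listings of abnormal values. Protocol 11.4 promises, for every analyte, by-arm numbers of subjects below or above the reference range.

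**The concern.** The TEMA limit for bilirubin and ALP (1.5 x ULN) sits below the entry cap (2 x ULN). A subject who enters between the two is already out of range under Table 5, and the rule has no clause for worsening. However far the value then rises, the TEMA count stays at zero.

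For bilirubin this means that a subject discontinued under the protocol's own liver rule can be missing from the SAP's main count of marked laboratory abnormality. A reader comparing arms in the any-time TEMA table would not know it.

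**Working it through.** The plan states no figure to reproduce here, so the check applies the rule as written.

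**1. The rule.** Let U and L be the Table 5 upper and lower limits. A high value is TEMA if

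post > U and (baseline missing, or L ≤ baseline ≤ U, or baseline < L).

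For bilirubin and ALP, L is N/A, so the last route is closed. With values in multiples of ULN the rule becomes

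post > 1.5 and (baseline missing or baseline ≤ 1.5).

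A baseline above 1.5 fails the second condition whatever the later value.

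**2. Which analytes have a gap.** A gap exists when U is below the entry cap of 2 x ULN.

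| Analyte | U (x ULN) | Entry cap | Baselines that can never be TEMA-high |
|---|---|---|---|
| ALT, AST, GGT | 3 | 2 | none among eligible subjects |
| Bilirubin | 1.5 | 2 | above 1.5, up to 2 |
| ALP | 1.5 | 2 | above 1.5, up to 2 |

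Only bilirubin also has a protocol discontinuation level.

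**3. Bilirubin values through the rule.**

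| Baseline (x ULN) | Post-baseline (x ULN) | TEMA? |
|---|---|---|
| 0.8 | 2.1 | yes |
| 1.5 | 2.1 | yes |
| 1.51 | 10 | no |
| 1.8 | 2.1 | no |
| 2.0 | 10 | no |

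On a grid of 50 baselines (1.51 to 2.00, step 0.01) and 299 post-baseline values (0.1 to 29.9, step 0.1), 50 × 299 = 14,950 pairs, none is TEMA.

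**4. Whether another laboratory table separates the case.** Subject A goes from 1.6 to a confirmed 2.5 x ULN. Subject B stays at 1.6.

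| Output | A | B |
|---|---|---|
| Protocol 3.3.1 bilirubin criterion met | yes | no |
| TEMA, any time | 0 | 0 |
| Above-normal incidence | 1 | 1 |
| Shift table | above to above | above to above |
| Protocol 11.4 out-of-range count | 1 | 1 |

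No laboratory count by arm distinguishes A from B. The descriptive range may show the extreme value, but it does not count subjects.

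**5. The SAP's neighbouring rules.** SAP 8.2 treats an event already present at first dose as treatment-emergent if its severity increases. SAP 8.4, Table 7, uses a change plus a threshold: systolic pressure going from 145 to 165 mmHg counts, since 165 − 145 = 20 and 165 > 140, although 145 was already high. The laboratory rule alone cannot register same-direction worsening.

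**6. Size per case.** With 137 subjects randomized 1:1, an arm has about 137 / 2 = 68.5. One omitted subject changes that arm's incidence by 1 / 68.5 = 1.5 percentage points. How many such subjects there are cannot be derived from the documents.

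**7. With a worsening clause.** Counting values above both baseline and 2 x ULN, baselines of 1.6, 1.8 and 2.0 rising to 2.1 are all counted. Subject B is still not counted.

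**8. Albumin (secondary).** SAP 8.3 lists albumin among the liver function tests, and its liver incidence table counts only values above normal. With an assumed range of 35–50 g/L (not in the documents) and baseline 42, values of 22, 28 and 33 g/L are in neither that table nor TEMA, 18 g/L is TEMA, and 51 g/L enters the above-normal table. The shift tables show the falls. The Protocol 11.4 by-arm count would include them, but SAP 8.3 does not repeat that count.

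**The case against.** **Most of the information survives elsewhere.** Subject A would be in the above-normal incidence, the ULN-standardized plots and the listings. Protocol 9.2.6 requires clinically relevant laboratory changes to be recorded as adverse events, so A should also reach the by-arm adverse event and discontinuation summaries of SAP 8.2 and the termination reasons of SAP 4.2. This stands. A reader might infer that a bilirubin stop would vanish from the report, or from every by-arm output; the documents do not support that. What is missing is a laboratory count that separates it.

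**The affected group is small and screened.** Exclusion 8 requires sponsor review and bars liver insufficiency, and inclusion 9 requires the investigator to judge abnormalities not clinically significant. This stands, and no frequency should be attached.

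**The known signal lies elsewhere.** A reader might infer that the gap hides the trial's identified liver signal. Protocol 16.1 names transaminases, which are unaffected, and Protocol 1.1 reports no ALP or bilirubin rise in study 42165279EDI1002. Bilirubin matters here because Protocol 3.3.1 gives it a discontinuation level.

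**An in-range baseline is a deliberate definition of treatment-emergent.** It does guard against counting pre-existing abnormality. It does not explain a limit set below the entry cap with no worsening clause, when SAP 8.2 and 8.4 both allow for worsening.

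**Albumin.** A reader might infer that the SAP counts albumin in the wrong direction throughout. It does not: Table 5 flags values below 20 g/L, and the shift tables have a below-range class. The point is confined to the liver incidence table, and that a fall is the direction of liver concern is general clinical knowledge that the documents do not state.

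**Conclusion.** The gap is real and follows from the documents without assumption: for bilirubin and ALP, no subject with a baseline above 1.5 and up to 2 x ULN can be TEMA-high. For bilirubin this includes a subject who meets the protocol's discontinuation criterion, and no planned laboratory table counts subjects above 2 x ULN by arm.

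The effect is confined to the laboratory counts. Each case is missed completely in the TEMA table, worth about 1.5 percentage points in an arm of about 68. Few cases are expected, but that is a judgement from the entry conditions, since no baseline distribution is given. No efficacy result or treatment decision depends on it. The albumin point is a matter of aligning the SAP with the protocol.

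**What to change.** In SAP 8.3, before database lock:

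- **Worsening clause.** For bilirubin and ALP with a baseline already above 1.5 x ULN, count a post-baseline value as TEMA if it exceeds both the baseline and 2 x ULN.
- **By-arm bilirubin count.** Add the number and percentage of subjects with total bilirubin above 2 x ULN at any time on double-blind treatment, regardless of baseline. Show it once for any value and once for values confirmed by repeat, since Protocol 3.3.1 requires confirmation.
- **Albumin alignment.** Carry the below-or-above-range counts by arm from Protocol 11.4 into SAP 8.3 and report low albumin there.

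The 2 x ULN cut is the protocol's own figure, used here only for counting. No entry or stopping rule changes.

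The cost is SAP wording and a few program lines, with no new data. The downside is that some ordinary fluctuation in subjects with raised baselines will be counted; this applies to both arms alike, and the confirmed-value row limits it.
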